# **3 STUDY DESIGN**

### 3.1 Description of Study Design

This is a Phase II, unblinded, randomized controlled trial of MMF withdrawal in patients with clinically quiescent SLE on longstanding MMF therapy (1000-3000 mg/day for at least one year in the case of extra-renal indication for MMF or for at least two years in the case of renal indications for MMF), who have been on stable doses of MMF, hydroxychloroquine or chloroquine, and corticosteroids (if applicable) for at least 12 weeks prior to randomization, and have an m-SLEDAI of < 4 at screening.

One hundred twenty eligible subjects will be randomized in a 1:1 ratio to one of the two study treatment arms below.

- MMF maintenance arm: These subjects will continue MMF treatment (1000-3000 mg/day) for the rest of their study participation (up to Week 60).
  - Baseline MMF dose = 3000 mg/day
    - Up to 60 weeks on 3000mg/day MMF
  - Baseline MMF dose = 2500 mg/day to 2750 mg/day
    - Up to 60 weeks on 2500mg/day MMF
  - Baseline MMF dose = 2000 mg/day to 2250 mg/day
     Up to 60 weeks on 2000mg/day MMF
  - Baseline MMF dose = 1500 mg/day to 1750 mg/day
     Up to 60 weeks on 1500mg/day MMF
  - Baseline MMF dose = 1000 mg/day to 1250 mg/day
    - Up to 60 weeks on 1000mg/day MMF

- MMF withdrawal arm: These subjects will taper off MMF over 12 weeks and remain off MMF for the rest of their study participation (up to Week 60 or until the primary endpoint of disease reactivation is met, whichever comes first).
  - Baseline MMF dose = 3000 mg/day
    - Four weeks on 1000 mg MMF twice a day (BID)
    - Four weeks on 1000mg (morning) & 500mg MMF (evening) QD
    - Four weeks on 500 mg MMF BID
    - Up to 48 weeks on no MMF
  - Baseline MMF dose = 2500 mg/day to 2750 mg/day
    - Four weeks on 1000mg MMF BID
    - Four weeks on 1000mg (morning) & 500mg (evening) MMF QD
    - Four weeks on 500 mg MMF BID
    - Up to 48 weeks on no MMF
  - Baseline MMF dose = 2000 mg/day to 2250 mg/day
    - Four weeks on 1000mg (morning) & 500mg (evening) MMF QD
    - Four weeks on 500mg MMF BID
    - Four weeks on 500 mg MMF QD
    - Up to 48 weeks on no MMF
  - Baseline MMF dose = 1500 mg/day to 1750 mg/day
    - Four weeks on 500mg MMF BID
    - Four weeks on 500 mg MMF BID
    - Four weeks on 500 mg MMF QD
    - Up to 48 weeks on no MMF
  - Baseline MMF dose = 1000 mg/day to 1250 mg/day
    - Four weeks on 500 mg MMF BID
    - Four weeks on 500 mg MMF QD
    - Four weeks on 500 mg MMF QD
    - Up to 48 weeks on no MMF

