### 5.3.1 Administration of Study Product in Response to SLE Reactivation

For subjects who experience clinically significant SLE reactivation (see Section 3.2 *Description of the Primary Endpoint*) before Week 60, the treatment should be guided by the following and the treating investigator's medical judgment:

- If the flare seems likely to respond to a burst of prednisone alone, the subject may continue on ALE06-provided MMF and the appropriate prednisone dose should be prescribed. If the subject has been withdrawn from MMF and the flare is likely to respond to a steroid burst alone, the appropriate steroid dose may be prescribed without additional immunosuppression.
- If the flare is not likely to respond to a burst of prednisone alone, then:
  - if the subject is taking MMF < 3000 mg/day, the subject will discontinue ALE06-provided study drug, and the subject should be prescribed MMF at a higher dose than what (s)he is currently taking. Other alternative or additional immunosuppressive therapy per investigator's discretion may be used. An appropriate steroid taper may be prescribed.
  - if the subject is currently taking MMF 3000 mg/day and the flare is so severe that either cyclophosphamide or adjunctive therapy plus MMF would be used, the subject will discontinue ALE06-provided study drug and the site principal investigator (PI) will prescribe immunosuppression as indicated. As guidance, BILAG\* A flares in Renal, Neuropsychiatric, or Hematological domains may represent such severe flares.

See Section 5.10, *Treatment Discontinuation and Subject Withdrawal* for additional information.

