#### 5.10.3 Safety Stopping Guidance

The DSMB will review any event that potentially impacts safety at the request of the protocol chair or DAIT/NIAID. The DSMB will have discretion to recommend actions regarding study conduct and continuation as a consequence of any planned or unplanned monitoring activity.

The DSMB will be informed in real time of the following event:

• Any immediately life-threatening event or death that occurs in the study, which is possibly, probably, or definitely related to study participation.

In addition, the following events will trigger both a comprehensive DSMB Emergency Safety Review and a temporary halt in enrollment:

- Events that result in permanent discontinuation of study intervention occurring in
  - 3 of the first 10 subjects randomized to the MMF withdrawal or
  - $\circ$  30% of subjects randomized to MMF withdrawal at any time point after the 11th subject is randomized.
- BILAG\* A flares occurring in
  - 3 of the first 10 subjects randomized to MMF withdrawal or
  - $\circ$  30% of subjects randomized to MMF withdrawal at any time point after the  $11^{\text{th}}$  subject is randomized.
- Severe SELENA-SLEDAI\* flares occurring in
  - 3 of the first 10 subjects randomized to MMF withdrawal or
  - $\circ$  30% of subjects randomized to MMF withdrawal at any time point after the  $11^{\text{th}}$  subject is randomized.

In the event of a temporary halt in enrollment, no new subjects will be consented, randomized or start on study product; subjects already on study product will continue unless they are the focus of the DSMB review. Subjects in the screening phase of the study may continue to undergo minimal risk procedures (e.g., blood tests), but more than minimal risk procedures should be deferred. Randomization will not occur until the DSMB review is complete. After careful review of the data, the DSMB will make recommendations regarding study conduct and/or continuation.

In addition, at each planned Data Review Meeting, the DSMB will review the estimated risk difference for disease reactivation (i.e. risk\_MMFwithdrawal - risk\_MMF maintenance) and consider whether or not the trial should be stopped for safety concerns. (See Section 8.4 *Interim Analysis* for details.)

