# 7.2. Primary Endpoint

# 7.2.1. Computation of the Primary Endpoint

The primary endpoint is the probability in each arm of experiencing clinically significant disease reactivation by 60 weeks after randomization. The 60-week time point is to allow 48 weeks of observation off MMF in the withdrawal arm and minimize dropout, which is likely to occur as the trial lengthens. Clinically significant SLE reactivation requires both:

- 1) A SELENA-SLEDAI\*-defined mild/moderate or severe flare, and
- 2) Increased immunosuppressive therapy on a sustained basis as defined by one of the following criteria:
  - a. Sustained activity: Subject has significant prolonged SLE flare requiring steroid increase/burst to ≥ 15 mg/day prednisone (or its equivalent) for more than four weeks.
  - b. Frequent relapsing/remitting:
    - Subject flares requiring an increase/burst of steroids and is successfully tapered to < 15 mg/day within four weeks, but this occurs on two or more occasions. or
    - ii. Intra-articular, intra-muscular or IV steroids, on more than one occasion.
  - c. Clinical activity of sufficient severity to warrant resumption of or an increased dose of MMF or addition of other major immunosuppressive including azathioprine or methotrexate. Regardless of steroid use, if the investigator observes disease activity of sufficient severity to warrant resumption, addition or increase in dosage of major immunosuppressant in the setting of a SELENA-SLEDAI\*-defined flare, subject has met the primary endpoint.

Version: 1.0 Page 16 of 48

\*ALE06 will typically use a spot urine protein:creatinine ratio rather than a 24-hour urine assessment for the SELENA-SLEDAI. However, if indicated, results from a 24-hour urine collection may be used.

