#### SELENA-SLEDAI:

The SELENA-SLEDAI instrument will be completed at baseline and every follow-up visit, including any Flare or Endpoint visits, during the course of the 60 week study period for all subjects. Data for this assessment will be collected on the *Physician's Global Assessment*, *SLEDAI*, and *SELENA Flare & Endpoint Assessment* CRF pages. The SELENA-SLEDAI assesses SLE disease activity and flares based on changes in the SLEDAI score, the Physician's Global Assessment (PGA), medication use (prednisone, NSAIDS, Plaquenil, major immunosuppressives), other disease activity criteria, and hospitalization due to SLE.

Study investigators complete the SLEDAI scale by indicating of presence of 24 SLE disease manifestations during the preceding 10 days. The original SLEDAI instrument includes an evaluation of proteinuria based on the protein:creatinine ratio derived from a 24-hour urine. For this study, the protein:creatinine ratio will typically be derived from the spot urine assessment although a 24-hour urine may be used if the spot urine assessment is not available. Each of the 24 disease manifestations has an assigned weight (see Appendix 14.3). The SLEDAI total score will be computed as the sum of the weights for the items indicated as present. If a component of the SLEDAI (urinalysis or hematological labs only) was missed at a visit, then the missing data will be imputed by using the last observation carried forward approach. If a component of the SLEDAI is missed over consecutive visits, then the subsequent components will not be imputed. If an entire visit was missed, the score will not be imputed.

Mild/moderate and severe SELENA-SLEDAI flares will be defined per the table below. If one or more criteria for a mild/moderate or severe flare have been met, a subject will be considered as having a mild/moderate or severe flare at that study visit.

MILD OR MODERATE FLARE		
	Change in SLEDAI > 3 points	
	New/Worse Discoid, photosensitive, profundus, cutaneous vasculitis, bullous lupus Nasopharyngeal ulcers	Pleuritis Pericarditis Arthritis
		Fever attributable to SLE
	Increase in prednisone, but not to > 0.5 mg/kg/day 	
	Added NSAID or Plaquenil	
	≥ 1.0 increase in Physician's Global Assessment (PhGA), but not to more than 2.5 (on a 3.0 indexed VAS scale—refer to the Physican's Global Assessment located on the Modified SLEDAl Source Document)	
SEVERE FLARE		
	Change in SLEDAI > 12	
	New/Worse CNS-SLE Vasculitis Nephritis Myositis	-0

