	Platelet Count < 60,000/ mm  [equivalent to 60 x1	0°/L]

Version: 1.0 Page 17 of 48

Hemolytic anemia with hemoglobin < 7% OR Decrease in hemoglobin > 3%  *Requiring: doubling of prednisone, prednisone > 0.5 mg/kg/day, and/or hospitalization
 Prednisone > 0.5 mg/kg/day 
New Cyclophosphamide (Cytoxan), Azathioprine, Methotrexate, Mycophenolate Mofetil, or hospitalization attributable to SLE
Increase in Physician's Global Assessment (PhGA) to > 2.5 (on a 3.0 indexed VAS scale—refer to the Physican's Global Assessment located
on the Modified SLEDAI Source Document)

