The total number of visits that a subject has with a SELENA-SLEDAI flare will be summarized by treatment group and overall. Summary tables detailing the reasons for mild/moderate or severe flares, along with reason for new or increased major immunosuppressives will be provided. Additionally, sensitivity analysis may be run to assess the impact of new or increased major immunosuppressives as the only cause of severe flare. Subjects who re-start

Version: 1.0 Page 21 of 48

or increase major immunosuppressives, but have no other disease activity that would categorize them as having a severe flare, will be categorized as not having a severe SELENA-SLEDAI flare and analyses would be replicated using this definition of a severe flare.

The study day of flare, type (mild/moderate or severe), and number of flares for each subject will also be shown graphically over time by subject and treatment group.

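### SAP 7.2.1 scores a restart of MMF as a severe flare and does not list an MMF increase, while later sections read as if both are scored; the severe-flare comparison needs one rule for both arms

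*SAP*

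**What the plan says.** - **Grading rule.** SAP 7.2.1 grades the visit as a flare "If one or more criteria for a mild/moderate or severe flare have been met". The severe list contains the row "New Cyclophosphamide (Cytoxan), Azathioprine, Methotrexate, Mycophenolate Mofetil, or hospitalization attributable to SLE". The same row stands in Protocol Appendix C and SAP 14.3. None of the three tables has a row for a higher dose of MMF.
- **Primary endpoint, limb 2c.** This limb pairs the two acts: "Clinical activity of sufficient severity to warrant resumption of or an increased dose of MMF or addition of other major immunosuppressive". Limb 1 separately requires a SELENA-SLEDAI flare.
- **Foreseen treatment.** For a subject taking MMF below 3000 mg/day whose flare is unlikely to respond to prednisone alone, Protocol 5.3.1 says "the subject should be prescribed MMF at a higher dose than what (s)he is currently taking" and adds "Other alternative or additional immunosuppressive therapy per investigator's discretion may be used".
- **Exposure in the withdrawal arm.** Protocol 3.1: "These subjects will taper off MMF over 12 weeks and remain off MMF for the rest of their study participation".
- **Sensitivity analyses.** SAP 7.3.2 says that a "sensitivity analysis may be run to assess the impact of new or increased major immunosuppressives as the only cause of severe flare", and SAP 7.3.3 repeats this for time to severe flare. Both would regrade subjects who restarted or increased a major immunosuppressive and had no other disease activity of severe grade. SAP 7.2.3 item 3 describes the parallel analysis for the primary endpoint, and there it is a commitment.
- **Use of the endpoint.** SAP 7.3.2 gives severe flare the same risk difference and confidence curve as the primary endpoint. It also plans tables of the reasons for flare and for new or increased immunosuppressives.

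**The concern.** The grading table and the sensitivity text do not agree on what is scored. The table names new MMF only. The sensitivity text removes flares that rest on a restart or an increase, which makes sense only if an increase can be scored in the first place. Nothing in the SAP says which wording governs, so two programmers could derive the endpoint differently.

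The choice matters because the two acts are tied to the randomised arm. After the taper, giving MMF to a withdrawal subject is a restart. Giving more MMF to a maintenance subject is an increase. If the table governs, severe flare partly records whether the subject was off MMF beforehand, which is the assignment itself. The error runs one way, against withdrawal. The analysis that would show its size is optional for severe flare and for time to severe flare.

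**Working it through.** **1. Check of the method on the plan's own figures.** Severe flare uses the primary endpoint's machinery, so the illustration below uses the normal approximation with unpooled variance and 60 per arm (120 subjects, 1:1, Protocol 8.1).

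- First cell of Protocol Table 8.1 (maintenance risk 0.05, increase 0.05, a = 0.15): SE = √(0.05×0.95/60 + 0.10×0.90/60) = 0.0479. Power = Φ((0.15 − 0.05)/0.0479 − 1.036) = 85.4%, against the stated 85%. All 22 filled cells reproduce within 2 points.
- Stated total of 390 for a = 0.10: per arm (1.036 + 0.842)² × (0.0475 + 0.09)/0.05² ≈ 194, total 388.

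No stated number is in error. The check only shows that the method matches the plan's.

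**2. The two readings side by side**, for a subject with no other severe criterion:

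| Event | Table wording only | Restart and increase both scored |
|---|---|---|
| Withdrawal subject, off MMF, MMF restarted | severe | severe |
| Maintenance subject, MMF raised | not severe | severe |
| Withdrawal subject still tapering, MMF raised | not severe | severe |
| New azathioprine, methotrexate or cyclophosphamide, or SLE hospitalisation, either arm | severe | severe |

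Only the first two rows separate the arms, and only under the table wording.

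**3. Size if the table governs (illustration).** Assumptions, none of them in the documents:

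- clinical severe-flare risk c = 0.05 in both arms;
- the same treatment-only rescue rate q in both arms, so the true difference is zero;
- a share s of maintenance rescues uses a newly listed agent, and the rest raise MMF;
- every withdrawal-arm rescue is scored, meaning that none falls in the taper.

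Scored risks are c + q (withdrawal) and c + qs (maintenance). The spurious difference is therefore q(1 − s). Confidence that the increase is ≤ 0.10 is Φ((0.10 − difference)/SE), taking observed risks equal to these values.

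| q | s | Spurious difference | Confidence, table wording | Confidence, both scored |
|---|---|---|---|---|
| 0.02 | 0 | 0.020 | 97% | 98% |
| 0.02 | 0.5 | 0.010 | 98% | 98% |
| 0.05 | 0 | 0.050 | 85% | 97% |
| 0.05 | 0.5 | 0.025 | 93% | 97% |
| 0.10 | 0 | 0.100 | 50% | 94% |
| 0.10 | 0.5 | 0.050 | 80% | 94% |

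Worked line, q = 0.05 and s = 0: risks 0.10 and 0.05, SE = 0.0479, Φ(0.05/0.0479) = 85%. With both scored: risks 0.10 and 0.10, SE = √(2×0.09/60) = 0.0548, Φ(0.10/0.0548) = 97%.

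**4. Size if increases are also scored.** Both arms have c + q, and the spurious difference is 0.

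**The case against.** The best reply is that the bias is one reading and not an established fact. Limb 2c treats resumption and increase alike. SAP 7.2.1 takes both from the same case report form page. Three sections of the SAP speak of restarting or increasing together. If the programming follows that intent, there is no artefact. This stands, and it is why the firm finding is an unresolved inconsistency with a conditional bias.

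Other limits also stand:

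- The higher-dose instruction in Protocol 5.3.1 is written for a subject taking MMF. A subject fully off it is not expressly covered there, and resumption is foreseen in limb 2c instead.
- Protocol 3.1.1 expects most flares early, and some may fall in the taper, when the asymmetry is absent.
- The planned tables of reasons will make treatment-only severe flares visible by arm, and the BILAG endpoints do not use the drug row. All secondary analyses are declared exploratory. The tables would not, however, correct the risk difference or the confidence curve.
- The size is the assumed rate by construction. SAP section 12 reports 8 of the first 80 subjects (10%) with reactivation by any route, so q = 0.10 in both arms would mean that essentially every reactivation was treatment-only. It is an outer case.

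Three stronger inferences are tempting and are not supported:

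- **That the primary endpoint is left exposed.** On the table wording a restart would supply limb 1 as well as 2c, and an increase only 2c. But SAP 7.2.3 item 3 commits to the analysis that tests this. Limb 1 also needs only a mild/moderate flare, which most subjects needing more treatment would probably meet on other criteria.
- **That safety monitoring is distorted between arms.** The severe-flare trigger in Protocol 5.10.3 is "30% of subjects randomized to MMF withdrawal at any time point after" the 11th subject is randomised. It counts one arm and makes no comparison, so the scoring of maintenance increases cannot affect it.
- **That other agents add to the asymmetry.** Protocol 5.6 lists prohibited medications and does not set out a rescue menu. Agents missing from the severe row are missing for both arms.

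**Conclusion.** The point holds as an inconsistency that needs a decision before the endpoint is derived. SAP 7.2.1 scores new MMF as severe and omits an increase; SAP 7.2.3, 7.3.2 and 7.3.3 read as if both are scored. If the table governs, the severe-flare risk difference is inflated against withdrawal by q(1 − s), which is 0.01 to 0.10 over the assumed ranges, and time to severe flare is shifted in the same direction. If increases are scored too, the artefact is zero. The documents do not allow the real size to be computed. A reader might infer a demonstrated bias, but the text does not support going that far.

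The reach is narrow: subjects off MMF, rescued with MMF, with no other severe criterion. Because the endpoint is secondary and exploratory, this is a worthwhile and cheap improvement, and it does not threaten the main result. Confidence is medium.

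**What to change.** 1. In SAP 7.2.1, state one rule that grades MMF resumption and MMF increase for SLE activity identically in both arms, so that both count or neither does. Align the wording of 7.2.3, 7.3.2 and 7.3.3 with it.
2. In SAP 7.3.2 and 7.3.3, replace the permissive wording with a commitment. The severe-flare and time-to-severe-flare analyses that drop flares resting only on a new, restarted or increased immunosuppressive should be run and reported beside the instrument version.

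The cost is SAP wording and one extra derivation. SAP 7.2.1 already takes MMF increase or resumption from the SELENA Flare & Endpoint Assessment page. There is precedent in the same section: the early-termination rules use a severe flare judged on clinical components without regard to treatment, and a footnote already adapts the prednisone criterion by duration. The small downside is a severe-flare definition that departs from the unmodified instrument, which is why both versions should be shown. The change affects scoring and reporting only.

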# **Increased immunosuppressive therapy:**

Increased steroid therapy, as defined by 2a and 2b in the definition of clinically significant SLE reactivation, will be taken from the SELENA Flare & Endpoint Assessment and Prior/Concomitant Medications CRF pages. To differentiate from any doses of steroids taken for non-SLE related causes, only records marked as "Yes" to the question "Is this medication a corticosteroid or immunosuppressant prescribed after Day 0 due to increased SLE activity?" will be analyzed. Prednisone started ≤10 days post-visit for a flare will be included as increased therapy.

Increase/resumption of MMF therapy or the addition of major immunosuppressive therapy, as defined by 2c in the definition of clinically significant SLE reactivation, will be taken from the SELENA Flare & Endpoint Assessment CRF page.

# **Endpoint:**

For each subject, a yes/no variable will be assigned to indicate whether a subject has met the primary endpoint of clinically significant disease reactivation between Day 0 and Week 60, as defined above.

Subjects who terminate early from the study, and who had not previously met primary endpoint, will be handled as follows:

- 1. Subjects who do not have a mild/moderate or severe SELENA-SLEDAI flare at their last study visit will be categorized as not experiencing clinically significant disease reactivation.
- 2. Subjects who have a mild/moderate or severe SELENA-SLEDAI flare at their last study visit:
  - a. Subjects will be categorized as experiencing clinically significant disease reactivation for the following three scenarios:
    - i. Subject has a SELENA-SLEDAI mild/moderate or severe flare at the time of early termination, and a steroid increase/burst to ≥ 15 mg/day prednisone that is sustained through end of study.
    - Subject previously experienced a flare requiring either intraarticular, intra-muscular or IV steroids, or an increase/burst of steroids that was successfully tapered to < 15 mg/day within four

Version: 1.0 Page 18 of 48

<sup>1 For ALE06, prednisone > 0.5 mg/kg/day is categorized as a severe SELENA-SLEDAI flare if the duration is >2 weeks. Increases in prednisone >0.5 mg/kg/day but for ≤2 weeks will be categorized as mild/moderate SELENA-SLEDAI flares.

weeks, and is experiencing a severe flare at the time of early termination.

- iii. Subject has a SELENA-SLEDAI severe flare based on the following clinical components: SLEDAI score; New/Worse disease, and Increase in PhGA without considering prednisone or other treatments
- b. Subjects experiencing flare at the time of early termination, but who do not met the criteria in 2.a. above, will be classified as not experiencing clinically significant disease reactivation.

These cases will be re-categorized under sensitivity analyses for the primary endpoint (see 7.2.3).

The time of clinically significant disease reactivation is defined as the date of the first SELENA-SLEDAI assessment that meets (or goes on to meet) the criteria for clinically significant SLE reactivation. The time-to-event will be defined as the interval: date of disease reactivation – date of Day 0 visit. Subjects who do not experience clinically significant disease will be censored at the last visit date on study.

The probability, or risk, of disease reactivation by Week 60 (on a 0 to 1 scale) in each arm will be derived using the Kaplan-Meier product-limit estimator for the cumulative incidence of disease reactivation. Standard errors and confidence intervals for the cumulative incidence will be obtained using Greenwood's formula.

